2.5 DATA HANDLING CONVENTIONS

2.5.1 General conventions

The following formulas will be used for computations of parameters.

Demographic formulas:

Age at baseline is calculated as follows:

$$\text{Age} = (\text{informed consent date} - \text{birth date})/365.25$$

BMI is calculated as follows:

$$\text{BMI} = \text{Weight in kg}/(\text{height}^2 \text{ in meters}).$$

2.5.2 Data handling conventions for secondary efficacy variables

SpO2

If SpO2 is missing, then that value will be imputed using last observation carried forward.

FiO2

FiO2 will be derived as following.

- For high flow nasal cannula, non-invasive ventilation, invasive ventilation, use FiO2 as reported on eCRF.
- For Nasal cannula, simple face mask, non-rebreather face mask, FiO2 will be converted based on below table.

Method	Oxygen flow rate O ₂ flow (l/min)	Fraction of Inspired Oxygen [FiO ₂] (%)
Nasal cannula	1	24
	2	28
	3	32
	4	36
	5	40
	6	44
	>=7	(O ₂ *4) + 20. Maximum will be 100
Simple face mask	5	40
	6	50
	7	55
	8	60
	9	65
	>=10	70
Non-rebreather face mask	<6	60
	6	60
	7	70
	8	80
	9	90
	10	95
	>=10	95

Note: If FiO₂ data is entered in the CRF for above devices, ignore value and derive as above. Some values for FiO₂ (not in the source table) are imputed according to a trend.

- If 'Other' oxygen device, use FiO₂ value if reported on eCRF. Otherwise, keep missing.
- If patient receives ECMO, alone or in combination with any other oxygen supplementation, use FiO₂ for ECMO only reported on eCRF.
- If patient is not on supplemental oxygen, impute with FiO₂=21%.

NEWS2

NEWS2 consists of 6 physiological parameters collected in various eCRF forms:

- Consciousness
- Respiratory rate
- Oxygen saturation (SpO₂)
- Pulse rate
- Systolic blood pressure
- Temperature

In addition, information on whether patients require supplemental oxygen and whether patient experienced chronic hypercapnic respiratory failure (collected in Pneumonia Status at Screening form) are required in the calculation of the NEWS2 score.

Calculation of NEWS2 score

NEWS2 score is calculated according to below chart.

- For patients with a history of or current chronic hypercapnic respiratory failure, use the dedicated section (SpO₂ Scale 2) in the chart.
- For patients who received oxygen supplementation, the score is uplifted by 2 points.

Physiological parameter	Score						
	3	2	1	0	1	2	3
Respiration rate (per minute)	≤8		9–11	12–20		21–24	≥25
SpO ₂ Scale 1 (%)	≤91	92–93	94–95	≥96			
SpO ₂ Scale 2 (%)	≤83	84–85	86–87	88–92 ≥93 on air	93–94 on oxygen	95–96 on oxygen	≥97 on oxygen
Air or oxygen?		Oxygen		Air			
Systolic blood pressure (mmHg)	≤90	91–100	101–110	111–219			≥220
Pulse (per minute)	≤40		41–50	51–90	91–110	111–130	≥131
Consciousness				Alert			CVPU
Temperature (°C)	≤35.0		35.1–36.0	36.1–38.0	38.1–39.0	≥39.1	

NEWS2 thresholds and triggers

NEW score	Clinical risk	Response
Aggregate score 0–4	Low	Ward-based response
Red score Score of 3 in any individual parameter	Low–medium	Urgent ward-based response*
Aggregate score 5–6	Medium	Key threshold for urgent response*
Aggregate score 7 or more	High	Urgent or emergency response**

* Response by a clinician or team with competence in the assessment and treatment of acutely ill patients and in recognising when the escalation of care to a critical care team is appropriate.

**The response team must also include staff with critical care skills, including airway management.

Imputation for NEWS2 component

If any component (physiological parameter) is missing, then that value will be imputed using last observation carried forward.

2.5.3 Missing data

For categorical variables, patients with missing data are not included in calculations of percentages unless otherwise specified. When relevant, the number of patients with missing data is presented.

Handling of medication missing/partial dates

No imputation of medication start/end dates or times will be performed. If a medication date or time is missing or partially missing and it cannot be determined whether it was taken prior or concomitantly, it will be considered a prior, concomitant, and posttreatment medication.

Handling of adverse events with missing or partial date/time of onset

Missing or partial adverse event onset dates and times will be imputed so that if the partial adverse event onset date/time information does not indicate that the adverse event started prior to treatment or after the treatment-emergent adverse event period, the adverse event will be classified as treatment-emergent. No imputation of adverse event end dates/times will be performed. These data imputations are for categorization purpose only and will not be used in listings. No imputation is planned for date/time of adverse event resolution.

Handling of adverse events when date and time of first investigational medicinal product administration is missing

When the date and time of the first IMP administration is missing, all adverse events that occurred on or after the day of randomization should be considered as treatment-emergent adverse events. The exposure duration should be kept as missing.

The last dose intake should be clearly identified in the case report form and should not be approximated by the last returned package date.

Handling of missing assessment of relationship of adverse events to investigational medicinal product

If the assessment of the relationship to IMP is missing, then the relationship to IMP has to be assumed and the adverse event considered as such in the frequency tables of possibly related adverse events, but no imputation should be done at the data level.

Handling of missing severity of adverse events

If the severity is missing for one of the treatment-emergent occurrences of an AE, the maximal severity on the remaining occurrences will be considered. If the severity is missing for all the occurrences a “missing” category will be added in summary table.

Handling of potentially clinically significant abnormalities

If a patient has a missing baseline he will be grouped in the category “normal/missing at baseline.”

For PCSAs with 2 conditions, one based on a change from baseline value or a normal range and the other on a threshold value, with the first condition being missing, the PCSA will be based only on the second condition.

For a PCSA defined on a threshold and/or a normal range, this PCSA will be derived using this threshold if the normal range is missing; eg, for eosinophils the PCSA is > 0.5 GIGA/L or $>ULN$ if $ULN \geq 0.5$ GIGA/L. When ULN is missing, the value 0.5 should be used.

Measurements flagged as invalid by the laboratory will not be summarized or taken into account in the computation of PCSA values.

Handling of missing discharge date

If a patient was discharged but the discharge date was missing, impute with last visit date.

2.5.4 Windows for time points

Visit windows based on days relative to the first IMP dose will be used to map the lab measurements to each scheduled visit (see [Appendix B](#)). The following rule will be applied when mapping the measurements to the visit:

1. For the same laboratory parameter, if a patient has more than one measurement at different dates within the same visit window, the scheduled measurement that is closest to the target date will be used (in case of tie select the latest). If there is no scheduled measurement within the visit window, the unscheduled measurement that is closest to the target date will be used (in case of tie select the latest).
2. When a patient has more than one measurement on the same lab parameter (or vital sign) on the same date, then the one with the later/largest sample ID will be used.

2.5.5 Unscheduled visits

Unscheduled visit measurements of laboratory data and vital signs will be used in PCSA analysis, computation of baseline, and will also be assigned to the appropriate visit window for the by-visit summaries.

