#### Protocol amendment summary of changes table

Section # and Name	Description of Change	Brief Rationale
Section 1.1 Synopsis, Section 1.2 Schema, Section 2.1 Study Rationale, Section 4.1 Overall Design, Section 4.2 Scientific Rationale for Study Design, Section 4.3 Justification for Dose, Section 6.1. Study Interventions administered (Table 3)	Closed enrollment to the sarilumab 200 mg IV arm	Based on anticipation of a more favorable benefit-risk profile in the 400 mg arm versus the 200 mg arm, enrollment in the 200 mg arm will be closed upon implementation of amended protocol 04.

Section # and Name	Description of Change	Brief Rationale
Section 1.3 Schedule of Activities	Urinalysis and urine culture results, serum IL-6, adverse events	The timing of urinalysis, urine culture results, serum IL-6, and adverse events assessments was clarified. No changes were made to the collection schedule.
Section 5.2	E04 was modified to clarify that oral corticosteroids were a type of systemic corticosteroids.	Clarification of definition.
Section 10.3.1 Definition of AE	Events meeting the AE definition: Removed: "Lack of efficacy" or "failure of expected pharmacological action" per se will not be reported as an AE or SAE. Such instances will be captured in the efficacy assessments. However, the signs, symptoms, and/or clinical sequelae resulting from lack of efficacy will be reported as AE or SAE if they fulfil the definition of an AE or SAE.	This bullet is duplicated in error. The same information is included in the first bullet.
Section 10.3.1 Definition of AE	Events meeting the AE definition: The signs, symptoms, and/or clinical sequelae resulting from lack of efficacy will be reported as AE or SAE if they fulfil the definition of an AE or SAE. Also, "lack of efficacy" or "failure of expected pharmacological action" also constitutes an AE or SAE.	This bullet is contradictory to the information provided, stating "Lack of efficacy" or "failure of expected pharmacological action" per se will not be reported as an AE or SAE.
Section 10.3.2.1 Recording and follow-up of AE and/or SAE	Added tables for assessment of intensity for infusion related reactions, hypersensitivity reactions, and neutropenia. Added guidance for the follow-up of AESIs of ALT increase and Grade 4 Neutropenia.	Provide guidance to the investigator.

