## Safety

The secondary safety endpoints are:

- Incidence of serious adverse events
- The incidence of major or opportunistic bacterial or fungal infections
- The incidence of major or opportunistic bacterial or fungal infections in patients with grade 4 neutropenia
- The incidence of hypersensitivity reactions, infusion reactions, gastrointestinal perforation
- White blood cell count, hemoglobin, platelets, creatinine, total bilirubin, alanine aminotransferase (ALT) on days 1, 4, 7, 15, 21, 29 (if still hospitalized)

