#### Outpatient (if possible):

- If not stabilized at discharge, follow up every 24 -72 hours, then every 2 weeks (when possible) until return to baseline and no manifestation of associated signs and symptoms.
- If stabilized, retest every 2 weeks if possible until results return towards baseline assuming no associated signs and symptoms.
- Consider consultation with a hepatologist and additional tests.

For AESI of Grade 4 Neutropenia (absolute neutrophil count less than <500/mm^3):

Inpatient:

- Confirmation of initial ANC within 24 -72 hours. Monitor patients for signs or symptoms of an opportunistic or nosocomial infection. Retest at least twice a week for the first week and then per standard of care until return to baseline or normal.
- If discharged, obtain neutrophil count on day of discharge and recommend follow-up with family doctor.

Outpatient (if possible):

- If the lab result has not stabilized at discharge, continue to monitor at least twice a week for the first week and then twice a month until return to baseline or normal as possible. Monitor patients for signs of infection.

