2.4.5.3 Analyses of laboratory variables

Hematology, blood chemistry and urinalysis are performed in local laboratories in this study.

The summary statistics (including number, mean, median, SD, minimum and maximum) of all laboratory variables (laboratory values and changes from baseline) will be calculated for each visit or study assessment (baseline, each post baseline time point, endpoint) by treatment group. This section will be organized by biological function as specified in [Section 2.1.4.3](#).

The incidence of PCSAs (list provided in [Appendix A](#)) at any time during the treatment-emergent adverse event period will be summarized by biological function and treatment group whatever the baseline level and/or according to the following baseline status categories:

- Normal/missing
- Abnormal according to PCSA criterion or criteria

The incidence of abnormal laboratory values at any time during the TEAE period will be summarized in shift tables by biological function and treatment group whatever the baseline level and/or according to the following baseline status categories:

- Normal/Missing
- Abnormal high according to the normal range
- Abnormal low according to the normal range

For parameters for which no PCSA criteria are defined, similar table(s) using the normal range will be provided.

For bacterial infection testing, results will be summarized as number of patients (counts and percent) with negative and positive levels by treatment group.

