Appendix B Visit windows based on day ranges

Table 4 – Time window for lab summaries

Visit Label	Target Day	Hematology, Chemistry	Bacterial infection testing
Daily follow-up until hospital discharge or Day 29			
Baseline	1	≤1	
Day 4	4	2-5	
Day 7	7	6-10	2-10
Day 15	15	11-17	≥11
Day 21	21	18-24	
Day 29	29	≥25	

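### Retests prompted by an abnormality after discharge can enter the Day 15, 21 and 29 laboratory means, although the protocol's laboratory endpoint covers hospitalized patients only

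*SAP*

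**What the plan says.** **What the endpoint covers.** The protocol synopsis lists white cells, hemoglobin, platelets, creatinine, bilirubin and "alanine aminotransferase (ALT) on days 1, 4, 7, 15, 21, 29 (if still hospitalized") as a secondary safety endpoint. Table 2 of the protocol repeats the restriction. Discharged patients need not come back, and their Day 29 contact is a phone call with no laboratory sample (synopsis; Schedule of Activities, footnote 4).

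**What is measured after discharge.** Protocol 8.2.4 asks that any laboratory test judged clinically significantly abnormal, during participation or up to 60 days after the last dose, be repeated until it normalizes, returns to baseline or loses its significance. The rule applies to every analyte and every arm. Protocol 10.3.2.1 adds outpatient follow-up for two AESIs. For ALT: "If stabilized, retest every 2 weeks if possible until results return towards baseline assuming no associated signs and symptoms". If ALT is not stable at discharge, testing is more frequent. Neutrophil counts that are not stable at discharge are also followed. The summary of changes for Amendment 04 records this as "Added guidance for the follow-up of AESIs of ALT increase and Grade 4 Neutropenia".

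**How results reach a visit.** SAP 2.5.5 says that unscheduled laboratory results "will also be assigned to the appropriate visit window for the by-visit summaries". SAP 2.5.4 gives priority to a scheduled result and then says: "If there is no scheduled measurement within the visit window, the unscheduled measurement that is closest to the target date will be used". The Appendix B table, "Time window for lab summaries", sets Day 15 as days 11-17, Day 21 as days 18-24 and Day 29 as day 25 or later. Its row heading reads "Daily follow-up until hospital discharge or Day 29".

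**What is reported.** Under SAP 2.4.5.3, summary statistics of values and changes from baseline "will be calculated for each visit or study assessment (baseline, each post baseline time point, endpoint) by treatment group".

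**The concern.** A patient discharged before Day 15 with normal results has no further scheduled laboratory test and drops out of the later windows. A patient discharged on the same day with an abnormal result may be retested, and the mapping rule places that retest in the Day 15, 21 or 29 summary. Among discharged patients, having a late value therefore depends largely on having had an abnormality. The late means then mix inpatients, who are the group the endpoint names, with outpatients selected for an abnormal test.

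At stake is how the late ALT, white cell and neutrophil summaries are read. Retests can keep a mean abnormal when inpatients have recovered. If one arm has more retests, or fewer inpatients to dilute them, the arms can differ at Day 21 or Day 29 even when their inpatients are alike. Unequal retest rates are plausible here: Protocol 2.3 expects a dose-related fall in neutrophils on sarilumab. SAP 2.4.7 also plans summaries of neutrophil counts by sampling point.

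**Working it through.** The plan states no figure for this point, so there is nothing to reproduce. The check has two parts.

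**1. Does the rule admit the values?** The Appendix B windows and the SAP 2.5.4 selection rule were applied to example patients discharged on Day 8, with scheduled samples on Days 1, 4, 7 and 8. The retest days are illustrative.

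| Retests after discharge | Day 7 window (6-10) | Day 15 window (11-17) | Day 21 window (18-24) | Day 29 window (25 or later) |
|---|---|---|---|---|
| Days 10, 13, 24, 38, 52 | Day 7, scheduled | Day 13 retest | Day 24 retest | Day 38 retest |
| Days 22, 36, 50 | Day 7, scheduled | none | Day 22 retest | Day 36 retest |
| None (no abnormality) | Day 7, scheduled | none | none | none |

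The Day 10 retest loses to the scheduled sample in its window. Day 38 is used for Day 29 because |38 - 29| = 9 is less than |52 - 29| = 23. Closing the Day 29 window alone would remove the Day 38 value but leave the Day 13 and Day 24 values in place.

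**2. How large could the effect be?** Let h be the share of an arm still in hospital with a value in the window, and q the share discharged with a retest in it. Arm size cancels, so:

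shift in the arm's mean = q / (h + q) x (retest mean - inpatient mean).

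Assumptions, none of them from the documents: inpatient mean ALT 1.0 x ULN in both arms; h = 10%, 20% or 40% in both arms; q = 10% on sarilumab and 3% on placebo; retest mean 1.5 or 3.0 x ULN. With h = 20%, the planned arm sizes of 160 and 80, and a retest mean of 1.5:

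- Sarilumab: 32 inpatients and 16 retests, 16/48 x 0.5 = 0.167.
- Placebo: 16 inpatients and 2.4 expected retests, 2.4/18.4 x 0.5 = 0.065.
- Gap: 0.102 x ULN.

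| h | Retest mean (x ULN) | Sarilumab shift | Placebo shift | Gap (x ULN) |
|---|---|---|---|---|
| 10% | 1.5 | 0.250 | 0.115 | 0.135 |
| 10% | 3.0 | 1.000 | 0.462 | 0.538 |
| 20% | 1.5 | 0.167 | 0.065 | 0.102 |
| 20% | 3.0 | 0.667 | 0.261 | 0.406 |
| 40% | 1.5 | 0.100 | 0.035 | 0.065 |
| 40% | 3.0 | 0.400 | 0.140 | 0.260 |

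With q = 5% and the same h in both arms, each mean still rises, by 0.056 (h = 40%, retest mean 1.5) to 0.667 (h = 10%, retest mean 3.0), but the gap is 0. With q = 5% in both arms and h = 10% in one and 20% in the other, the gap is 0.167 - 0.100 = 0.067 at a retest mean of 1.5, and 0.667 - 0.400 = 0.267 at 3.0. Equal retest rates are therefore not enough; the inpatient shares must match too.

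**The case against.** **The retests may be few or never reach the dataset.** Outpatient testing is guidance, to be done where possible. For neutropenia it applies only to counts not stable at discharge. Neither document says that results from outside the hospital enter the by-visit laboratory data, and SAP 2.1.4.3 describes hematology and chemistry collection as running to Day 29 or discharge. This stands: the enrichment is a possibility, not a certainty. The Appendix B row heading points the same way, but it labels the rows and is not written as an exclusion.

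**Late retests should drift toward normal.** Follow-up runs until recovery, so some values will be close to baseline. This also stands, and it favors the lower end of the range. Part of any gap may also come from a true excess of events. The mean would then exaggerate a real signal that the AESI and PCSA tables already show.

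**The late means are already selected.** They come from patients still in hospital. That is correct, and the fix does not change it, but that selection is part of the endpoint as defined. The retests add a second one that the plan does not declare.

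**Two stronger readings are not supported.** A reader might infer that only patients with an ALT or neutropenia AESI are retested after discharge. Protocol 8.2.4 covers any clinically significant abnormal test, and readmitted patients can also supply late samples. The 8.2.4 rule widens the selection on abnormality; it does not remove it.

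A reader might also infer that this sampling began with Amendment 04, which closed the 200 mg arm, so that the arm is sampled on a different basis. The change table for that amendment lists no change to 8.2.4 or to the AESI follow-up in 8.3.3, and both cover all arms. Patients on 400 mg or placebo randomized before the amendment are in the same position as those on 200 mg.

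**Conclusion.** The point holds as a gap in the SAP's data-handling rules. As written, SAP 2.5.4, SAP 2.5.5 and Appendix B let abnormality-triggered results from discharged patients into the Day 15, 21 and 29 laboratory summaries, against the in-hospital limit of the protocol's endpoint. The SAP's version history ends on 05-May-2020, before the AESI retest guidance of 11-Jun-2020, so its rule was not written with that guidance in view.

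Whether the means are in fact distorted depends on outside results being recorded. An artificial difference between arms also needs retest rates or inpatient shares to differ. The documents give neither, so the size cannot be fixed; the 0.07-0.54 x ULN range rests wholly on the assumptions listed. The affected outputs are descriptive. The primary and key secondary tests are untouched, and PCSA incidence and the AESI summaries do not depend on the visit mapping. The correction is worth making because it is cheap and brings the summary back to its stated endpoint.

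**What to change.** - In SAP 2.5.4 and 2.5.5, limit the by-visit laboratory summaries to samples taken while the patient is hospitalized. Include the discharge sample and any sample from a readmission that falls within the window. A cut at first discharge would wrongly drop the readmission samples.
- In Appendix B, give the Day 29 window an upper bound. Day 33, for example, would mirror the four days allowed before the target (29 - 25 = 4).
- Keep post-discharge retests for the PCSA analysis, the AESI listings and the description of resolution.

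The cost is a sentence or two in the SAP and a filter on hospitalization dates. The late by-visit summaries will hold slightly fewer values. The filter also relies on discharge dates, and SAP 2.5.3 imputes a missing one with the last visit date. If that visit were a follow-up phone call, retests could still pass the filter, so imputed dates should be flagged.

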2.5.6 Pooling of centers for statistical analyses

Not applicable.

3 INTERIM ANALYSIS

An interim analysis is planned to be performed when approximately 50% of total planned number of patients (~200) are randomized. The efficacy endpoints will be analyzed using the same methods described in the efficacy analyses section ([Section 2.1.3](#)). The key secondary endpoint will be modified to be the percent of patients alive at Day 15.

The purpose of the interim analyses is to obtain an understanding of the possible drug effect in the population under study. An administrative alpha of 0.001 will be spent at interim analysis. Due to the conservative amount of alpha spent at interim, no alpha adjustment will be made for the primary analysis when the last patient randomized of the whole study reaches Day 29 (or planned Day 29 if the patient is discharged or leaves the study early), or the supportive final analysis at Day 60.

The interim analyses will be performed by an external statistical analysis center which is separate from personnel involved in the trial conduct. The unblinded results can only be viewed by a small group of senior sponsor individuals, who are separate from sponsor personnel involved in the conduct of the study. People involved in the conduct of the study (Patients, Investigators, Study Team, and Project Team) will have no access to the interim analysis results. Sponsor may decide to make changes to the dose and/or alter disease category based on the interim results.

The interim analysis is planned to mainly include the following:

- Demographics and baseline characteristics
- 7-point ordinal scale (observed value and change from baseline category, time to improvement of at least two points, proportion of patients with at least 2-point improvement)
- Patient survival status
- Overview of TEAE
- Number of patients with SAE

